Appendix VII – WHO performance status

Clinical performance status

- 0 Able to carry out all normal activity without restriction.
- 1 Restricted in physically strenuous activity but ambulatory and able to carry out light work.
- 2 Ambulatory and capable of all self-care but unable to carry out any work; up and about more than 50% of waking hours.
- 3 Capable only of limited self-care; confined to bed or chair more than 50% of waking hours.
- 4 Completely disabled; cannot carry out any self-care; totally confined to bed or chair.

Appendix VIII – Cockcroft & Gault formula

- The estimated GFR is given by:

$$\text{Males: } \frac{1.25 \times (140 - \text{age}) \times \text{weight (kg)}}{\text{serum creatinine } (\mu\text{mol/l})}$$

$$\text{Females: } \frac{1.05 \times (140 - \text{age}) \times \text{weight (kg)}}{\text{serum creatinine } (\mu\text{mol/l})}$$

- This formula usually under-estimates GFR by 10-30% compared with EDTA or measured 24-hour creatinine clearance, so is used in this trial as a screening test.
- A Cockcroft/Gault estimate of ≥ 50 ml/min is accepted as evidence of adequate renal function.
- Patients with a Cockcroft/Gault estimate of < 50 ml/min prior to randomisation should have formal GFR measurement with EDTA or 24 urinary creatinine, which must be within the normal range. The corrected EDTA clearance should be ≥ 50 ml/min.
- After the start of treatment, if the Cockcroft/Gault estimate falls by $>25\%$ from baseline or to below 50 ml/min, the formal EDTA measurement should be re-checked.

Appendix IX – EORTC QLQ questionnaires

ENGLISH

EORTC QLQ-C30 (version 3)

We are interested in some things about you and your health. Please answer all of the questions yourself by circling the number that best applies to you. There are no "right" or "wrong" answers. The information that you provide will remain strictly confidential.

Please fill in your initials:

--	--	--	--	--

Your birthdate (Day, Month, Year):

--	--	--	--	--	--	--	--	--	--

Today's date (Day, Month, Year):

31

--	--	--	--	--	--	--	--	--	--

	Not at All	A Little	Quite a Bit	Very Much
1. Do you have any trouble doing strenuous activities, like carrying a heavy shopping bag or a suitcase?	1	2	3	4
2. Do you have any trouble taking a long walk?	1	2	3	4
3. Do you have any trouble taking a short walk outside of the house?	1	2	3	4
4. Do you need to stay in bed or a chair during the day?	1	2	3	4
5. Do you need help with eating, dressing, washing yourself or using the toilet?	1	2	3	4

During the past week:

	Not at All	A Little	Quite a Bit	Very Much
6. Were you limited in doing either your work or other daily activities?	1	2	3	4
7. Were you limited in pursuing your hobbies or other leisure time activities?	1	2	3	4
8. Were you short of breath?	1	2	3	4
9. Have you had pain?	1	2	3	4
10. Did you need to rest?	1	2	3	4
11. Have you had trouble sleeping?	1	2	3	4
12. Have you felt weak?	1	2	3	4
13. Have you lacked appetite?	1	2	3	4
14. Have you felt nauseated?	1	2	3	4
15. Have you vomited?	1	2	3	4
16. Have you been constipated?	1	2	3	4

Please go on to the next page

During the past week:

	Not at All	A Little	Quite a Bit	Very Much
17. Have you had diarrhea?	1	2	3	4
18. Were you tired?	1	2	3	4
19. Did pain interfere with your daily activities?	1	2	3	4
20. Have you had difficulty in concentrating on things, like reading a newspaper or watching television?	1	2	3	4
21. Did you feel tense?	1	2	3	4
22. Did you worry?	1	2	3	4
23. Did you feel irritable?	1	2	3	4
24. Did you feel depressed?	1	2	3	4
25. Have you had difficulty remembering things?	1	2	3	4
26. Has your physical condition or medical treatment interfered with your family life?	1	2	3	4
27. Has your physical condition or medical treatment interfered with your social activities?	1	2	3	4
28. Has your physical condition or medical treatment caused you financial difficulties?	1	2	3	4

For the following questions please circle the number between 1 and 7 that best applies to you

29. How would you rate your overall health during the past week?

1 2 3 4 5 6 7

Very poor

Excellent

30. How would you rate your overall quality of life during the past week?

1 2 3 4 5 6 7

Very poor

Excellent

Additional Questions

During the past week:

	Not at all	A little	Quite a bit	Very much	Not applicable
31. Have you had a dry and/or sore mouth?	1	2	3	4	
32. Have you had problems eating or drinking because of a sore mouth?	1	2	3	4	
33. Have you had difficulty handling small objects (e.g. doing up buttons or zips)?	1	2	3	4	
34. How much has your treatment interfered with your normal daily activities?	1	2	3	4	N/A

Since you started chemotherapy:

35. How worthwhile do you think your treatment has been?	1	2	3	4	N/A
--	---	---	---	---	-----

Over the past 6 weeks:

36. How many times have you been visited by your GP?	
37. How many times have you visited your GP?	
38. How many times have you been visited by a district nurse?	
39. How many times have you been visited by a MacMillan nurse?	

The aim of this questionnaire is to measure how much any skin problem you may have experienced has affected your life OVER THE PAST WEEK.

	Not at all	A little	A lot	Very much	Not applicable
40. Over the last week, how itchy, sore, painful or stinging has your skin been?	1	2	3	4	
41. Over the last week, how embarrassed or self conscious have you been because of your skin?	1	2	3	4	
42. Over the last week, how much has your skin interfered with you going shopping or looking after your home or garden?	1	2	3	4	N/A
43. Over the last week, how much has your skin influenced the clothes you wear?	1	2	3	4	N/A
44. Over the last week, how much has your skin affected any social or leisure activities?	1	2	3	4	N/A
45. Over the last week, how much has your skin made it difficult for you to do any sport?	1	2	3	4	N/A
46. Over the last week, has your skin prevented you from working or studying?	Yes	No			N/A
If "No", over the last week how much has your skin been a problem at work or studying?	1	2	3		
47. Over the last week, how much has your skin created problems with your partner or any of your close friends or relatives?	1	2	3	4	N/A
48. Over the last week, how much has your skin caused any sexual difficulties?	1	2	3	4	N/A
49. Over the last week, how much of a problem has the treatment for your skin been, for example by making your home messy, or by taking up time?	1	2	3	4	N/A

**EORTC QLQ – LMC21**

Patients sometimes report that they have the following symptoms or problems. Please indicate the extent to which you have experienced these symptoms or problems during the past week. Please answer by circling the number that best applies to you.

During the past week :	Not at all	A little	Quite a bit	Very Much
50. Have you had trouble with eating?	1	2	3	4
51. Have you felt full up too quickly after beginning to eat?	1	2	3	4
52. Have you worried about losing weight?	1	2	3	4
53. Have you had problems with your sense of taste?	1	2	3	4
54. Have you had a dry mouth?	1	2	3	4
55. Have you had a sore mouth or tongue?	1	2	3	4
56. Have you been less active than you would like to be?	1	2	3	4
57. Have you had tingling hands or feet?	1	2	3	4
58. Have you had pain in your stomach area?	1	2	3	4
59. Have you had discomfort in your stomach area?	1	2	3	4
60. Have you been bothered by your skin or eyes being yellow(jaundiced)?	1	2	3	4
61. Have you had pain in your back?	1	2	3	4
62. Have you felt "slowed down"?	1	2	3	4
63. Have you felt lacking in energy?	1	2	3	4
64. Have you had trouble having social contact with friends?	1	2	3	4
65. Have you had trouble talking about your feelings to your family or friends?	1	2	3	4
66. Have you felt stressed?	1	2	3	4
67. Have you felt less able to enjoy yourself?	1	2	3	4
68. Were you worried about your health in the future?	1	2	3	4
69. Were you worried about your family in the future?	1	2	3	4
During the past four weeks:				
70. Have you been bothered by the effect of the disease or treatment on your sex life?	1	2	3	4

Appendix X – EQ-5D questionnaire

By placing a tick in one box in each group below, please indicate which statements best describe your own health state today.

Mobility

- I have no problems in walking about
- I have some problems in walking about
- I am confined to bed

Self-Care

- I have no problems with self-care
- I have some problems washing or dressing myself
- I am unable to wash or dress myself

Usual Activities (*e.g. work, study, housework, family or leisure activities*)

- I have no problems with performing my usual activities
- I have some problems with performing my usual activities
- I am unable to perform my usual activities

Pain/Discomfort

- I have no pain or discomfort
- I have moderate pain or discomfort
- I have extreme pain or discomfort

[figure not shown]
Anxiety/Depression

- I am not anxious or depressed
- I am moderately anxious or depressed
- I am extremely anxious or depressed

To help people say how good or bad a health state is, we have drawn a scale (rather like a thermometer) on which the best state you can imagine is marked 100 and the worst state you can imagine is marked 0.

We would like you to indicate on this scale how good or bad your own health is today, in your opinion. Please do this by drawing a line from the box below to whichever point on the scale indicates how good or bad your health state is today.

Your own health state today

Appendix XI – NCI common terminology criteria for adverse events (v3.0)

Toxicity	0	1	2	3	4	5
NAUSEA	None	Loss of appetite without alteration in eating habits	Oral intake decreased without significant weight loss, dehydration or malnutrition; IV fluids indicated < 24hrs	Inadequate oral caloric or fluid intake; IV fluids, tube feedings, or TPN indicated ≥ 24hrs	Life-threatening consequences	Death
VOMITING	None	1 episode in 24 hours	2-5 episodes in 24 hours; IV fluids indicated < 24hrs	≥ 6 episodes in 24 hours; IV fluids, or TPN indicated ≥ 24hrs	Life-threatening consequences	Death
ANOREXIA	None	Loss of appetite without alteration in eating habits	Oral intake altered without significant weight loss or malnutrition; oral nutritional supplements indicated	Associated with significant weight loss or malnutrition; IV fluids, tube feedings or TPN indicated	Life-threatening consequences	Death
ALOPECIA	Normal	Thinning or patchy	Complete	-	-	-
RASH: ACNE/ ACNEIFORM	None	Intervention not indicated	Intervention indicated	Associated with pain, disfigurement, ulceration, or desquamation	-	Death
RASH: HAND-FOOT SKIN REACTION	None	Minimal skin changes or dermatitis (e.g., erythema) without pain	Skin changes (e.g., peeling, blisters, bleeding, oedema) or pain, not interfering with function	Ulcerative dermatitis or skin changes with pain, interfering with function	-	-
NAIL CHANGES	None	Discoloration; ridging (koilonychias); pitting	Partial or complete loss of nail(s); pain in nailbed(s)	Interfering with ADL	-	-
PAIN	None	Mild pain not interfering with function	Moderate pain: pain or analgesics interfering with function, but not interfering with ADL	Severe pain: pain or analgesics severely interfering with ADL	Disabling	-
MUCOSITIS/ STOMATITIS (clinical exam)	None	Erythema of the mucosa	Patchy ulcerations or pseudomembranes	Confluent ulcerations or pseudomembranes; bleeding with minor trauma	Tissue necrosis; significant spontaneous bleeding; life-threatening consequences	Death
MUCOSITIS/ STOMATITIS (functional/ symptomatic)	None	Minimal discomfort, intervention not indicated	Symptomatic, medical intervention indicated but not interfering with ADL	Stool incontinence or other symptoms interfering with ADL	Symptoms associated with life-threatening consequences	Death
DIARRHOEA (patients without colostomy)	None	Increase of <4 stools/day over baseline	Increase of 4-6 stools/day over baseline; IV fluids indicated < 24hrs	Increase of ≥ 7 stools/day; incontinence; IV fluids ≥ 24hrs; hospitalisation	Life-threatening consequences (e.g., haemodynamic collapse)	Death
DIARRHOEA (patients with a colostomy)	None	Mild increase in ostomy output compared with baseline	Moderate increase in ostomy output compared with baseline, not interfering with ADL	Severe increase in ostomy output compared to baseline, interfering with ADL	Life-threatening consequences (e.g., haemodynamic collapse)	Death
LETHARGY	None	Mild fatigue over baseline	Moderate or causing difficulty performing some activities	Severe fatigue interfering with ADL	Disabling	-
HAEMO- GLOBIN	Within normal limits	10.0g/dl - normal	8.0 - 9.9g/dl	6.5 - 7.9g/dl	<6.5g/dl	Death
PLATELETS	Within normal limits	75x10 ⁹ /l - normal	50 - 74x10 ⁹ /l	25 - 49x10 ⁹ /l	<25x10 ⁹ /l	Death
NEUTROPHILS	Within normal limits	1.5x10 ⁹ /l - normal	1.0 - 1.4x10 ⁹ /l	0.5 - 0.9x10 ⁹ /l	<0.5x10 ⁹ /l	Death
ALT	Within	>ULN - 2.5 x ULN	> 2.5 - 5.0 x ULN	> 5 - 20.0 x ULN	> 20 x ULN	-

	normal limits					
AST	Within normal limits	>ULN – 2.5 x ULN	> 2.5 – 5.0 x ULN	> 5 – 20.0 x ULN	> 20 x ULN	-
BILIRUBIN	Within normal limits	>ULN – 1.5 x ULN	> 1.5 – 3.0 x ULN	> 3 – 10.0 x ULN	> 10 x ULN	-
SENSORY NEUROPATHY	Normal	Asymptomatic; loss of deep tendon reflexes or paresthesia (including tingling) but not interfering with function	Sensory alteration or paresthesia (including tingling), interfering with function, but not interfering with ADL	Sensory alteration or paresthesia interfering with ADL	Disabling	Death
MOTOR NEUROPATHY	Normal	Asymptomatic; weakness on exam/testing only	Symptomatic weakness interfering with function, but not interfering with ADL	Weakness interfering with ADL; bracing or assistance to walk indicated	Life-threatening; disabling (e.g., paralysis)	Death
ALLERGIC REACTION/HYPER-SENSITIVITY (INCLUDING DRUG FEVER)	Normal	Transient flushing or rash; drug fever < 38°C (<100.4°F)	Rash; flushing; urticaria; dyspnea; drug fever ≥38°C (≥104°F)	Symptomatic bronchospasm, with or without urticaria; parenteral medication(s) indicated; allergy-related edema/angioedema; hypotension	Anaphylaxis	Death
MAGNESIUM, SERUM LOW (HYPOMAGNES-EMIA)	Within normal limits	<LLN - 1.2 mg/dL <LLN - 0.5 mmol/L	<1.2 - 0.9 mg/dL <0.5 - 0.4 mmol/L	<0.9 - 0.7 mg/dL <0.4 - 0.3 mmol/L	<0.7 mg/dL <0.3 mmol/L	Death

- *These are selected categories. For full list see <http://ctep.cancer.gov/reporting/ctc.html>*

Appendix XII – Economic evaluation

1. Overview

The economic evaluation will take the form of a cost-effectiveness analysis. The differential cost of the alternative treatments will be related to their differential benefits in terms of quality-adjusted life years (QALYs), and standard cost-effectiveness acceptability curves will be used to show the probability of one option being more cost-effective than the others.

2. Estimating costs

All significant NHS resource consumption that is expected to differ between treatment options will be estimated within the study. This will include hospital and non-hospital costs. In addition, we will record patient borne travel costs to attend hospital appointments. These are dealt with in turn below.

2.1 Hospital resource use

Within the trial, hospital resource use data will be collected on all patients entering the trial. These will be collected using case record forms completed at clinical review at 12 weekly intervals. Some visits to and stays in hospital may relate to non-study hospitals. To ensure that data on this form of resource use are captured, a questionnaire will be administered to patients as part of the QoL assessments at baseline and 12-weekly.

These resources will be valued in monetary terms using unit costs representative of UK practice at the time of analysis. For drugs, this will be based on British National Formulary prices. For hospital procedure and hotel costs, unit costs will if available, be based on NHS Reference Costs. If not available, these will be based on nearest appropriate equivalent.

2.2 NHS non-hospital resource use

Patients' use of community-based NHS (and complementary health) services will be collected from patients in the form of a short questionnaire administered at 12 weekly intervals. The resources will include visits to and from a GP or district nurse. Costing of community-based resources will be based on published unit costs. Other services will be costed using data available at the point of analysis.

2.3 Patient travel costs

Patients' travel costs will be estimated using a cost per hospital visit and multiplying that cost by the number of occasions each patient visits hospital. In order to cost a given visit to hospital for each patient, specific questions will be asked of each patient at baseline. This will collect information on the typical mode(s) of transport, distance and time of journeys to hospital, and whether the patient had a companion. Based on these data, patients' travel costs will be based on published unit costs for travel.

Questions will also be asked at baseline to collect information to cost the time patients and any companions allocate to the visit. Time will be valued using an average national wage rate with

sensitivity analysis used to explore the implications of valuing the time of patients who are not in employment differently from those that are in employment.

3. Measuring effects

The clinical trial is estimating a range of clinical and Health Related Quality of Life (HRQL) effects in trial patients. The purpose of the economic evaluation will be to set these in context of the resource costs incurred in achieving them. The cost-effectiveness analysis will relate differential cost to an aggregated measure of effect in the form of a quality-adjusted life-year (QALY).

4. Analysis

All resource use data will be valued in monetary terms as described above such that each patient has a cost over the period of follow-up. A full stochastic analysis will be undertaken to allow for sample variation in resource use and effect data. Methods are altering quickly in this area and, by the time of the analysis, 'best practice' may have altered markedly from today. If such an analysis were to be undertaken now, the general methods would be as follows.

Allowance will have to be made – both for the costs and effects – for censored data due to differential follow-up and the fact that it is unlikely that all patients would have died at the point of analysis. For effects, these methods are clear and established using standard methods of survival analysis. For costs, methods are now available for handling censored data⁵.

Although cost data are likely to be heavily skewed, it is important that means are reported as this is the relevant statistic for decision makers. Parametric methods or non-parametric bootstrapping will be used as appropriate.

For the cost-effectiveness analysis, two analyses will be undertaken (one taking a health care system perspective on costs, the other a societal perspective). QALYs will be the measure of effectiveness.

A QALY profile will be estimated for each patient based on their survival duration weighted by their responses to the EQ-5D HRQL questionnaire, which generates a single index value for health at each point of follow-up⁶. The profiles will assume a straight-line relationship between the index value at time t and the value at time $t+1$. The number of QALYs they experience during the period of follow-up in the trial will be the area under the QALY profile.

In the primary analysis only data collected in the trial will be used in the analysis; in other words, the estimate of QALYs for each group is likely to reflect the fact that some patients are still alive after the year's follow-up (i.e. the survival curve is truncated and survival techniques will be used to estimate QALYs).

As a secondary analysis, extrapolation techniques will be used to estimate the final portion of the curve so as to provide a full estimate of differential life expectancy. A range of extrapolation techniques exists, with currently no consensus as to the best. The methodological literature will be monitored.

Cost-effectiveness acceptability curves will be used to facilitate a measure of uncertainty around cost-effectiveness estimates¹. These curves show the probability of one form of management

being more cost-effective than the others assuming alternative levels of the maximum amount decision-makers are willing to pay for an extra QALY.

Sensitivity analysis will be used to consider the importance of sources of uncertainty other than sample variation (e.g. unit costs, discount rates, cost perspective). Multiple regression techniques will be employed to provide as precise a measure of cost-effectiveness as possible and to undertake sub-group analysis using baseline patient characteristics that will be defined in advance in the analysis plan.

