The incremental cost per life year and per QALY will be estimated, initially at 3 years but also at 5 years and 10 years. Longer term survival will be modelled using time to event analysis, supplemented eventually by actual survival data (using The Health and Social Care Information Centre tagging of patients). Differences in the quality of life of treated patients compared to controls will be estimated by use of EQ5D, the standard instrument. Costs will be from the societal perspective and besides the cost of antibody treatment will include use of all hospital resources, NHS non-hospital resources and subject travel costs. See Appendix XII for more details.

17. Molecular pathological research

New EPOC will parallel and complement COIN in its translational intention. Three parallel translational studies will be undertaken.

The first is a focused, in depth study investigating the relationship between DNA repair capacity and chemotherapy response and side effects. This will increase the power to detect differences between the effect of SNPs in the DNA repair genes on response and toxicity (as per COIN trial protocol).

Secondly, this study uses Cetuximab without prior exclusion of patients whose tumours do not express EGFR on immunohistochemistry. We will therefore collect tumour samples from redundant stored paraffin embedded tissue to evaluate the presence of the EGFR and other downstream markers, in an attempt to define molecular correlates with response to Cetuximab (as per COIN trial protocol).

Thirdly, the trial provides a unique opportunity to collect fresh tumour tissue in order to undertake cDNA microarray analysis and further analyses related to EGFR pathway functions and response to therapy.

17.a Blood and tumour sample collection

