0:00-2:00	Cetuximab 500 mg/m ² IV infusion, 0.5-2 hours (see below) Flush line with 0.9% saline
2:00-3:00	Observe for delayed hypersensitivity reaction
3:00	Flush line with 5% DDextrose
3:00-5:00	L -folinic acid (175 mg flat dose) or d,l -folinic acid (350 mg flat dose) IV infusion, 2 hrs, 250 ml 5% Dextrose Concurrently with:
3.00-5:00	Oxaliplatin 85 mg/m ² IV infusion, 2 hrs, 250 ml 5% Dextrose
5:00	Flush line with 5% DDextrose
5:00-5:05	5-Fluorouracil 400 mg/m ² IV bolus over 5 minutes
5:05-51:00	5-Fluorouracil 2400 mg/m ² IV infusion over 46 hours
51:00	Disconnect pump and flush line (5 ml heparinised saline)
Day 4-14	No treatment

Notes:

- The 1st dose of Cetuximab (500 mg/m²) should be administered by i.v. infusion **over 120 minutes**. There must be at least one hour between completion of Cetuximab and the start of chemotherapy.
- The 2nd dose of Cetuximab (500 mg/m²) should be administered by i.v. infusion **over 90 minutes**. There must be at least one hour between completion of Cetuximab and the start of chemotherapy.

- **Subsequent doses** of Cetuximab (500 mg/m²) should be administered by i.v. infusion **over 60 minutes**. There must be at least one hour between completion of Cetuximab and the start of chemotherapy.
- Bolus 5FU is recommended to be given over 5 minutes but may be administered as a 15 or 30 minute infusion where this reflects local practice.
- Because of a potential in vitro chemical reaction between Oxaliplatin and chloride ions, care is taken to avoid contact with normal saline in the drip-tubing etc.
- Oxaliplatin may cause vein pain, which is helped by applying an electric heat pad over the vein throughout the 2-hour infusion. Suitable therapeutic heat pads are available from Winterwarm® (38x30cm, model HP5/LT) or Dimplex® (38x28cm) each costing under £20. If this fails extending the infusion time to 4-6 hours may be helpful.
- Do not use injection equipment containing aluminium.
- The use of pre-packed 'minibags' of 5FU is acceptable.
- Please check with the UoSCTU if your local policy for pre-chemotherapy medication differs to that stated here to confirm if it is acceptable for use in the trial.

Oral antiemetics (starting day 2):

- Dexamethasone 4 mg tds x1 day; 4 mg bd x1 day; 4 mg od x1 day.
- Domperidone or Metoclopramide prn.

Note on the use of dexamethasone

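### Visit time for the societal costing comes from baseline questions, so the extra 2 to 3 hours of a combined cetuximab and chemotherapy visit is not captured

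*Protocol*

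**What the plan says.** Section 16 sets the frame: "Costs will be from the societal perspective and besides the cost of antibody treatment will include use of all hospital resources". Appendix XII section 4 then plans two cost-effectiveness analyses, one from the health care perspective and one from the societal perspective.

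Appendix XII section 2.3 estimates travel costs "using a cost per hospital visit and multiplying that cost by the number of occasions each patient visits hospital". To obtain that unit cost, "specific questions will be asked of each patient at baseline"; these cover transport mode, distance, journey time and whether a companion came. A second paragraph deals with time: "Questions will also be asked at baseline to collect information to cost the time patients and any companions allocate to the visit". It adds: "Time will be valued using an average national wage rate", with a sensitivity analysis on how the time of patients not in employment is valued.

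Other resource use is followed over time. For care at non-study hospitals, section 2.1 states that "a questionnaire will be administered to patients as part of the QoL assessments at baseline and 12-weekly", and section 2.2 collects community service use every 12 weeks. For visit time, baseline is the only collection point given.

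Appendix I places cetuximab before the same chemotherapy that Arm A receives, with infusions of 120, 90 and then 60 minutes in the dose notes, and requires a gap: "There must be at least one hour between completion of Cetuximab and the start of chemotherapy".

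**The concern.** A baseline answer cannot describe a visit that has not yet happened. Whatever form is used, the time questions precede the first trial infusion. If they are asked with the baseline quality-of-life form, they also precede randomisation, because sections 11.c and 15.c require that form first. The answer then cannot depend on the allocated arm, and randomisation makes its expected value equal in the two arms.

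Multiplying by the number of visits does not recover the difference, since treatment is scheduled fortnightly in both arms. The planned sensitivity analysis in section 2.3 varies the value of an hour, not the number of hours by arm. The extra on-site time falls only on Arm B, so leaving it out understates the incremental societal cost of cetuximab. A larger sample would not remove the error. Cost-effectiveness is secondary aim 3.

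**Working it through.** **Inputs (Protocol)**
- OxMdG timetable, Appendix I: 120 min infusion + 5 min bolus; 46 h pump starts at 2:05.
- IrMdG timetable, Appendix I: 30 + 120 + 5 min; pump starts at 2:35.
- Cetuximab dose notes, Appendix I, both backbones: 120 min (dose 1), 90 min (dose 2), 60 min (later doses), each followed by at least 60 min before chemotherapy.
- Planned treatment, section 2: 12 + 12 weeks in two-week cycles = 12 cycles.
- Antibody cost, section 16: about £20,000 per patient.
- Wage: not given. Assumed £10 to £20 per hour.

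**Reproducing the plan's timetable.** Arm B minutes to pump start = Arm A minutes + cetuximab infusion + 60.
- OxMdG, dose 1: 125 + 120 + 60 = 305 min = 5:05, as printed.
- IrMdG, dose 1: 155 + 120 + 60 = 335 min = 5:35, as printed.

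**Extra time per combined visit** = cetuximab infusion + 60 min.

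| Dose | Extra | OxMdG, A vs B | IrMdG, A vs B |
|---|---|---|---|
| 1 | 3.0 h | 125 vs 305 min | 155 vs 335 min |
| 2 | 2.5 h | 125 vs 275 min | 155 vs 305 min |
| 3 on | 2.0 h | 125 vs 245 min | 155 vs 275 min |

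**Per Arm B patient**
- 12 cycles: 3.0 + 2.5 + 10 × 2.0 = 25.5 h; with a companion at every visit 2 × 25.5 = 51 h.
- 8 cycles: 3.0 + 2.5 + 6 × 2.0 = 17.5 h.

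**In money, 12 cycles**
- Patient alone: 25.5 × £10 to £20 = £255 to £510.
- With companion: 51 × £10 to £20 = £510 to £1,020.
- Share of antibody cost: 255 / 20,000 = 1.3% up to 1,020 / 20,000 = 5.1%.

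**An inconsistency that affects the input.** The OxMdG plus cetuximab timetable also prints a range of 0.5 to 2 hours for the infusion. At its lower end the extra time would be 0.5 + 1 = 1.5 h per visit. This entry and the 120/90/60 minute dose notes must be reconciled before either is used for costing. The figures above follow the dose notes.

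**The case against.** The strongest reply is that section 2.3 does not fix as much as this. The unit cost multiplied by visits is stated for travel. Time has its own paragraph, which says only that baseline questions will supply information for costing it and then turns to wage and employment. That wording could describe valuation inputs alone, leaving on-site duration to an economic analysis plan. The questions themselves are not reproduced: the forms in Appendices IX and X contain no visit-time items. Section 4 of the appendix adds that methods may have changed by the time of analysis.

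Part of this stands. Applying the multiplication to time is a close reading, not explicit text. But baseline is the only source given for time, no route to an arm-specific duration is described, and sections 2.1 and 2.2 show that repeat collection was specified where it was wanted. Followed as written, the method does not pick up the difference.

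Two stronger readings should be resisted. A reader might infer that visit time doubles in Arm B. The timetables give scheduled minutes to pump connection only; they leave out the journey, clinical review and any wait for blood results, so the proportional rise in whole-visit time is smaller. A reader might also infer that an inpatient stay would be costed as one visit of baseline length. The protocol does not say so: section 2.1 separates visits from stays, and hotel costs are valued in their own right.

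The 12-cycle total is also an upper figure. Section 9.b makes treatment depend on toxicity, performance status and patient choice, and Appendix I provides for withheld doses and for stopping cetuximab. Section 9.b also lets cetuximab continue after chemotherapy stops, and such a visit is not 2 to 3 hours longer than a chemotherapy visit.

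**Conclusion.** The point holds as a small bias of known direction. Appendix XII section 2.3, on its natural reading, gives both arms the same expected time per visit, although Appendix I schedules 3.0, 2.5 and then 2.0 h more for each combined cetuximab visit. The shortfall is up to 25.5 h per Arm B patient over 12 full cycles and 17.5 h over 8, and less where cetuximab is withheld or stopped.

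The money figures rest on an assumed wage of £10 to £20 per hour and full treatment; the top of the range also needs a companion at every visit. The result, about 1.3% to 5.1% of the antibody cost, touches the societal analysis only. The health care perspective is unaffected, and nothing here shows that the cost-effectiveness conclusion would change. It is worth correcting because the remedy is cheap.

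**What to change.** In Appendix XII section 2.3 or the economic analysis plan, limit the baseline questions to transport mode, distance, journey time, companion and employment status. Cost on-site time for infusion visits separately, by arm, backbone and dose number, from the Appendix I scheduled durations, or from recorded times where available; section 11.e already has cetuximab administration details recorded for Arm B, though it does not say that times are included. Multiply by the visits actually made, and treat cetuximab-only visits as their own type. Reconcile the infusion range in the OxMdG plus cetuximab timetable with the dose notes first.

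This takes a few lines of costing rules and needs no new data from patients. The cost is slightly more work in the economic analysis and a societal cost per QALY that becomes slightly less favourable to cetuximab.
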